## 3. Study Design

#### 3.1. Sample Size

Primary outcome for the RCT is the ITT- analysis of the between-group difference in change in KOOS4 from baseline to the 2-year follow-up.

We wanted to detect a 10-points difference ( $\Delta$ ) with a standard deviation (SD) of 15, with a level of power ( $\beta$ ) of 90% and a level of significance ( $\alpha$ ) of 0.05. The calculation was performed using this formula, where the f ( $\alpha$ ,  $\beta$ ) is a constant (given by Stuart J. Pocock; "Clinical trials. A practical approach":

 $2 \times SD^2 / \Delta^2 \propto f(\alpha, \beta) = 2 \times 15^2 / 10^2 \times 10.5 = 47.25 \approx 48$  (patients in each group)

Estimated dropout rate at 2 years was 15%, thereby, the number of subjects (N) randomized was to be:

N - (15 % out of N) = 47.25 $N = 55.6 \approx 56 \text{ (patients in each group)}$ 

Thus, 112 patients randomized to two groups are necessary for the ITT-analysis.

#### 3.2. Randomization and Blinding

The schedule for randomization was randomly generated using a computer before the initiation of the trial. To conceal the outcomes of the randomization, the allocation numbers were put in concealed, opaque C5 envelopes. An independent staff member prepared the envelopes. These were kept in a locked location accessible only by one research assistant. Following the informed consent and completion of the baseline measures, the envelopes were opened by the patients and the allocation was revealed.

The randomization was stratified for gender, to ensure equal gender distribution in the two groups. In both genders there were used block randomization with blocks of eight.

The randomization was not stratified for center, because initially the trial was planned to be finalized in one hospital only; the Oslo University Hospital (OUH). Due to less patient flow than suspected, the recruitment was after patient number 53 taken over by Martina Hansens Hospital (MHH). The recruitment started at OUH in October 2009 and continued after patient number 54 at MHH from May 2011 and finished (patient number 140) in September 2012.

All patients went through baseline and follow-up tests at NIMI (Norsk Idrettsmedisinsk Institutt), Ullevål, Oslo. Patients randomized to arthroscopy were treated in the respective hospital that they were recruited from, and patients randomized to exercise therapy went through the interventions at NIMI (patients recruited between patient number 1 and 83) or at Gnist Trening og Fysioterapi, Bærum, an external physiotherapist institute.

Equality in patient treatment in the two interventional hospitals and two physiotherapist institutes respectively, was considered extremely important, especially on account of the lack of randomization stratification for center. Similarity in the recruitment and treatment procedures was ensured by written procedures and protocols and head-to-head instructions and dialogues. Only one surgeon was involved in recruiting at OUS, and another one at MHH. Fifty-four out of the total 64 (84 %) surgical procedures were performed by these two surgeons. Equivalently, the exercise therapy was performed by one dedicated physiotherapist in each institute, following similar procedures and protocols.

The RCT is a single-blinded study. The outcome assessor was blinded to group allocation, was not involved in providing the interventions, and unaffiliated with the treatment sites. The participants, the project physiotherapist and the surgeons delivering part of the interventions could not be blinded.

The statistician performing the statistical analyses will be blinded to group allocation.

Järvinen et al have estimated that blinded interpretation of study results feasibly and

effectively might diminish interpretation bias. Therefore, the writing committee of this study (see section 7) will, prior to breaking the code, conduct three interpretations of the results, one assuming that *Group I* was randomized to exercise, and the other assuming that Group I was randomized to arthroscopy, and *Group II* to the opposite intervention. In this superiority trial there are three possible results;

- 1) Group I is statistically superior to Group II
- 2) Group II is statistically superior to Group I
- 3) No statistically significant difference between the groups

Until the writing committee has agreed in writing on the clinical interpretation of the results the randomization code will not be broken, ensuring that bias during data interpretation is kept to a minimum.

## 4. Study Population

#### 4.1. Subject Disposition

Study procedures, including recruitment strategies and inclusion and exclusion criteria, have been described in the PhD protocol (Appendix 1). Patients included in the trial were randomized to: A) Exercise therapy or B) Arthroscopic partial meniscal resection. All consecutive patients who came to the two inclusion sites on the days of the orthopedic surgeons outpatient clinic fulfilling the eligibility criteria were asked to enter the study. Patients fulfilling all eligibility criteria, but refusing to participate in the randomization, were registered.

Crossovers are a common problem in studies randomizing to surgical or non-surgical treatments. In this study participants who experienced impairment of their symptoms or lack of improvement during the 2-year observation period, were reassessed at any time when necessary by the orthopedic surgeon who was responsible for the study. Indication for surgery (crossing over from exercise to arthroscopy) or re-operation (meniscal re-resection or other surgery in the index knee within 2 years) was based upon patient's history, clinical and radiological examinations.

Patients from the arthroscopy group that had postoperative active exercise therapy supervised by a physiotherapist more than 80 % of twice a week in 12 weeks (19 or more sessions)(equivalent to 80 % in the exercise group) were regarded as crossing over to the exercise group.

The frequency of crossovers from exercise to arthroscopy and vice versa, re-operations with meniscal re-resections or other surgery in the index knee within 2 years will be registered and reported (Table 3).

# 5. Statistical Analysis

# 5.1. Primary Endpoint

In this RCT, the primary outcome is the between-group difference in change in  $KOOS_4$  from baseline to 2-year follow-up. p-values and 95% CI for the main outcome will be presented to assess superiority. An independent statistician will analyze the primary outcome.

Multiple regression analysis will be made using a mixed model (MM) ANOVA (analysis of variance) in all patients randomized data set (APRS). In this model, patient is the random factor and time points (baseline, 3, 12 and 24 months), treatment arm (exercise, arthroscopy) and recruitment site (OUH, MHH) are fixed factors. Gender, a randomization stratification factor will be encountered for to avoid variance. Furthermore interactions between the fixed factors will be included in the model.

To reduce the variance, results of continuous variables will be adjusted for baseline imbalance.

Preconditions for multiple regression analysis are independency, normal distribution and constant variance of the residuals. This will be checked in SPSS by plotting a histogram over standardized residuals, a normality plot for standardized residuals and a plot with standardized residuals contra standardized predictive value. SPSS will make a list of residuals larger then 3 and smaller than -3.

Different statistical analysis software will be used; SPSS, Stata, SAS.

The program code for the analysis of the primary outcome is in SAS:

PROC MIXED; CLASS TREAT TIME CENTRE; MODEL CHANGE= BASELINE\*TIME TREAT\*TIME CENTRE SEX TIME; REPETED TIME / SUBJECT=PATIENT TYPE=UN; RUN;

TREAT is the treat variable, TIME is nominal time since baseline in months, CENTER indicates center, CHANGE is change from baseline in KOOS4, BASELINE is KOOS4 at baseline, SEX is the patients gender, and PATIENT is the patient's id.

## 5.2. Secondary Endpoints

Secondary outcomes are between- and within-groups comparisons of the change from baseline to the 2-year follow-up in all secondary endpoints except for the isokinetic muscle strength and functional performance data, where 1-year follow-up is the end point.

All outcomes will be checked for normality and statistical methods will be dependent on data distribution. When fulfilling the requirements for regression analyses, ANOVA analyses of the ITT populations will be conducted; otherwise non-parametrical tests will be used.

Finally, PP- and AT-analyses will be conducted in a range of secondary outcomes.

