#### 2.1. Primary Objective and Outcome

The primary objective is to compare difference in change in knee function measured by KOOS4 from baseline to the 2-year follow-up (including follow-ups at 3 months and 1 year) between patients randomized to exercise therapy or arthroscopic partial meniscal resections. The reason for choosing this primary endpoint is as follows:

The KOOS is a knee-specific instrument, developed to assess the patients' opinion about their knee and associated problems. The KOOS evaluates both short-term and long-term consequences of knee injury. The KOOS subscales has previously been found reliable and are validated for patients with a range of knee injuries including those having knee arthroscopy and those with knee OA.

The KOOS holds 42 items in 5 separately scored subscales; Pain, other Symptoms, Function in daily living (ADL), Function in Sport and Recreation (Sport/Rec), and knee-related Quality of Life  $(QOL)^{26}$ . Each item in KOOS is scored from 0-4 on a Likert scale. Subscale scores are given separately (see www.koos.nu for user's guide and scoring) ranging from 0 (worst) to 100 (best). In this study, each subscale except ADL will be calculated according to the instructions in the user's guide and the composite KOOS4 will be calculated giving each subscale equally large impact on the KOOS4 score using this formula:

KOOS4 = (KOOS Pain + KOOS Symptoms + KOOS Sport/Rec + KOOS QOL)/4

An average KOOS score derived from any number of calculated subscales scores can be used as primary endpoint in an RCT, if defined a priori. However, since  $KOOS_4$  has not been subjected to psychometric validation, they are intended for statistical purposes only and cannot be interpreted clinically. The individual KOOS subscales must be analyzed as secondary outcomes to enable clinical interpretation of the contributions of each subscale of the KOOS score.

One reason for choosing a composite KOOS score as the primary endpoint is to avoid issues with *multiplicity*. Another reason is to avoid bias between groups because *group belongingness* only may favor scores in some KOOS subscales. The third reason is that especially the KOOS subscale ADL has *low effect size* and is actually not optimal for measuring differences in knee function when analyzed in this patient population. The assumed group belongingness bias and effect size difficulties will be discussed below:

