## 2.7. Specification of Endpoints

#### 2.7.1. Primary Endpoint

The trial is designed as a superiority trial, i.e. we expect that one of the treatment groups will improve more than the other group in the primary outcome  $KOOS_4$  from baseline to the primary endpoint after 2 years. Thereby, the primary endpoint is based upon the between-group difference in change in  $KOOS_4$ .

The primary analysis of the primary outcome (KOOS4) will be analyzed in an intention-totreat (ITT) analysis. It implies that for all patients randomized to one treatment, should be analyzed according to the treatment to which the patient was allocated, irrespective of whether they received this or some other treatment, or no treatment at all (Figure 2). The purpose of this ITT principle is to preserve the theoretical basis for the validity of the statistical results, specifically by eliminating the possibility that patients with known or unknown prognostic factors are systematically selected to a treatment.

The *ITT population* is equal to all patients randomized to the two treatment arms, and the dataset is equal to the "all patients randomized set" (APRS).

Missing values due to patients' absence from follow-ups or withdrawal from the study are not uncommon in clinical trials. Several approaches are described for handling missing data in the ITT analysis, and among them "last observation carried forward" (LOCF) (the last observed outcome is regarded as the final outcome), multiple imputation (MI) (stochastic technique which depends on model-based imputation of multiple values for each missing observation) and mixed model (MM) analysis. A MM analysis includes all patients with at least one baseline or follow-up value, and includes both fixed and random factors. The MM method is shown to have higher statistical precision in analyzing data from an RCT, than LOCF or MI methods. Therefore, MM method is chosen for the analysis of the primary outcome in this trial.

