The KOOS subscales Pain, Symptoms, ADL, Sport/Rec and QOL, EQ- 5D Index, EQ-5 VAS, weight and global knee function will be presented as mean (with 95% CI) for each treatment group. Between-group differences in change from baseline to 2 years will be statistically assessed. Each subscale of the KOOS will be presented graphically for its development over the 2 years period.

All issues during the trial found in the treatment records from the project physiotherapist, hospital records or the questionnaire from the follow-ups will be assessed to determine whether it represents an AE or not. AE will be presented in a table (see Table 1) and analyzed statistically by comparing actual numbers of serious AE (site other than index knee, index knee and all serious events) and non-serious AE (site other than index knee, index knee and all serious events).

AE associated with surgery will be given in Table 1 for the following groups:

1. Those receiving arthroscopic meniscal resection by randomization

2. All treatment dependent AE reported during and after surgery in those who had surgery even though randomized to the exercise therapy throughout the follow up period

AE associated with exercise therapy will be given in Table 1 for the following groups:

1. Those remaining in the 'Exercise therapy' group throughout the follow up period

2. All treatment dependent AE reported prior to the surgery in those who had surgery even though randomized to the exercise therapy

3. Those randomized to surgery but crossing over to exercise during the follow-up period

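### Section 5.2 lets a normality check choose the secondary analysis without tying it to the KOOS4 model, and a transition rating is analysed as change from baseline

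*SAP*

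**What the plan says.** **Choice of method.** Section 5.2 opens its methods with "All outcomes will be checked for normality and statistical methods will be dependent on data distribution" and continues: "When fulfilling the requirements for regression analyses, ANOVA analyses of the ITT populations will be conducted; otherwise non-parametrical tests will be used". It gives no criterion for the check, no named non-parametric test, no covariates, no effect measure and no handling of missing visits.

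**Primary model.** Section 2.7.1 discusses missing data and concludes: "Therefore, MM method is chosen for the analysis of the primary outcome in this trial". The SAS code in 5.1 models change in KOOS4 at each follow-up, with baseline by time, treatment by time, centre, sex and time, and an unstructured covariance within patient.

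**Role of the subscales.** Section 2.1 defines KOOS4 as a plain average of four subscales. It says KOOS4 itself cannot be interpreted clinically and that the subscales have to be analysed so that their contributions can be. Table 4 lists mean change with 95% CI for each subscale and has a column for the between-group difference.

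**Global knee rating.** Section 2.2 defines five categories from much better to much worse. Section 2.7.2 says that "weight and global knee function will be presented as mean (with 95% CI) for each treatment group" and then calls for between-group differences in change from baseline to 2 years. Section 5.2 sets the same change for every secondary endpoint except strength and performance. Table 2 lists the rating at baseline. Table 4 heads it as mean, median and range, at 1 year.

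**The concern.** The subscales carry the clinical reading of KOOS4, so they need the same kind of estimate as KOOS4. The rule in 5.2 can give one subscale an adjusted mean difference from a repeated-measures model and another a p-value from a rank test. PP and AT analyses are planned as well, so the same subscale could also take different routes in different populations. At stake are precision and a common scale for explaining the primary result.

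The rating is a separate matter. A category such as much better already compares now with before. Subtracting a baseline rating from a 2-year rating takes a change of a change, measured from two different reference points. The visit at which it is to be reported is also unclear.

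**Working it through.** **1. The plan's own figure.** Section 3.1 uses a difference of 10, SD 15, 90% power and alpha 0.05: 2 × 15² / 10² × 10.5 = 47.25, so 48 per arm. Then 47.25 / 0.85 = 55.6, so 56 per arm. Both reproduce. No power is stated for any secondary outcome.

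**2. Inputs for the subscale comparison.**
- Patients: 140 randomised (section 1) and 15% dropout (3.1) give 140 × 0.85 / 2 = 59.5, about 60 per arm.
- SD of change: 15, the KOOS4 figure in 3.1, borrowed for a subscale.
- Difference: 7.5 points (assumed).
- Correlation r between baseline and 2-year score: 0.3 to 0.7 (assumed).

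**3. Formula.** With equal variances at both visits, adjusting for baseline multiplies the variance of the change-score comparison by (1 + r)/2. Power is Φ(7.5/SE − 1.96), with SE = 15 × √(2v/60).
- Unadjusted, v = 1: SE 2.739, ratio 2.739, power 78%.
- r = 0.3, v = 0.65: SE 2.208, ratio 3.397, power 92%.
- r = 0.5, v = 0.75: SE 2.372, ratio 3.162, power 89%.
- r = 0.7, v = 0.85: SE 2.525, ratio 2.970, power 84%.

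**4. Simulation** (3,000 trials per setting, bivariate normal scores, 60 per arm):

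| r | Rank test on change | Unadjusted change | Baseline-adjusted |
|---|---|---|---|
| 0.3 | 75% | 77% | 92% |
| 0.5 | 74% | 76% | 88% |
| 0.7 | 76% | 77% | 84% |

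Omitting baseline costs 7 to 15 points. Ranking costs a further 1 to 2.

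**5. The rule itself.** A second simulation (48 per arm, 2,000 runs per setting) applied a Shapiro-Wilk check at 5% to the residuals of change, then a t-test or a Mann-Whitney test.
- Power of the two-stage rule was within about 0.2 points of the plain t-test on change.
- Type I error was 0.044 to 0.062. The Monte Carlo standard error is √(0.05 × 0.95 / 2000) = 0.005. In the setting that gave 0.062, the plain t-test also gave 0.062 and the adjusted analysis 0.061, so the excess is not due to the check.
- With an assumed ceiling at 100, the unadjusted comparison lost about 19 to 24 points of power against the adjusted one, for differences of 7 and 10 points.

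**6. Common scale.** KOOS4 is an average, so on the same patients the four subscale differences in mean change average exactly to the KOOS4 difference. If each subscale is adjusted for its own baseline, the match is close rather than exact. A rank statistic has no such relation.

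**7. Global rating.** Simulated under proportional odds, 48 per arm, odds ratios 2 to 3, two assumed category distributions, and a baseline rating independent of the 2-year rating:
- rank comparison of the 2-year rating: power 40% to 81%;
- mean of the 2-year rating: 35% to 78%;
- mean change from baseline: 21% to 54%.

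Taking change instead of the 2-year rating costs about 17 points (45.6 − 28.2) to 35 points (74.2 − 39.3). Using a mean in place of ranks at 2 years costs far less, 2 to 8 points.

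**8. Visit.** Section 2 says the 2-year survey left out only strength and performance tests, so the rating should exist at 2 years. Sections 2.7.2 and 5.2 use 2 years; Table 4 says 1 year.

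**The case against.** The strongest reply is that 5.2 already means the 5.1 model. Section 5.1 calls its model a mixed-model ANOVA and a multiple regression, and lists regression preconditions; 5.2 then speaks of regression requirements and ANOVA. Section 5.1 also says, in general terms, that "results of continuous variables will be adjusted for baseline imbalance". This is a fair reading, and on it the ANOVA branch is sound. But 2.7.1 ties the mixed model to the primary outcome and 5.2 does not refer back, so the text leaves the matter open. A reader might infer that the subscales are definitely not analysed with the KOOS4 model; the SAP does not support that.

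A reader might also put the loss at 19-38% of patients, from the relative efficiency (3/π)(1 + r)/2 = 0.62 to 0.81. That figure compares a rank test with an adjusted model on normal data, which the rule would seldom send to a rank test. Ranking alone contributes 3/π = 0.955; the rest is the baseline covariate. Nor do the simulations support a claim that the check distorts error rates.

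Section 2.7.2 and Table 4 ask for means with confidence intervals whatever the distribution, so a rank p-value might sit beside them rather than replace them. That softens the loss of a common scale, but p-value and interval would then come from different analyses. The SAP names no rank test, so the loss of covariates and repeated measures assumes an ordinary one.

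For the rating, Table 4 does have rows for the five categories, and 5.2 could send it to a valid rank test. The mean, the change from baseline and the conflicting visit remain. Finally, secondary outcomes are supportive only, and the analyst works on coded arms, which limits steering.

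**Conclusion.** The point holds for secondary outcomes only; the primary KOOS4 analysis is untouched. For the subscales, the defect is an open choice of method. On the non-parametric branch, an ordinary rank test on change drops the baseline, sex and site terms and the repeated measures, and gives no mean difference to set beside KOOS4. On the ANOVA branch this happens only if the 5.1 model is not meant. The size is roughly 7 to 15 points of power from omitting baseline plus 1 to 2 from ranking, at 60 per arm. It rests on an assumed 7.5-point difference, assumed correlations of 0.3 to 0.7 and the KOOS4 SD of 15 applied to a subscale. The normality check itself costs almost nothing in power or type I error.

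For the global rating, a change from baseline has no clear meaning whatever the power figures, which depend on assumed distributions. The 1-year and 2-year labels contradict each other.

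**What to change.** - State in 5.2 that the KOOS subscales and other continuous secondary outcomes use the baseline-adjusted repeated-measures model of 5.1, whatever the normality plots show. Strength and performance run to 1 year. The SF-36 summaries, which section 2 limits to baseline and 2 years, use the single-visit form.
- Replace the non-parametric branch for these outcomes with a bootstrap or robust-standard-error check when residuals are skewed.
- Analyse the global rating as an ordinal outcome at 2 years, by proportional odds or a rank test, with n and % per category. Either method is acceptable if named in advance.
- Delete the mean and change from baseline for the rating in 2.7.2, Table 2 and Table 4, exempt it from the change rule in 5.2, and reconcile the visit label in Table 4.

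The cost is a few sentences and re-use of the primary code. No new data are needed.

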## 6. Major Protocol Deviations

In the Clinical Trial document (registration number NCT01002794) published in October 25. 2009 before the start of inclusion of patients the primary outcome is settled as "KOOS", not more specified. In the PhD-protocol (April 2012) the composite KOOS4, (an averaged score of the four KOOS subscales: Pain, Symptoms, Sport and Recreation and QOL) was decided as the primary outcome for the RCT.

There is no major difference between this SAP and the PhD-protocol dated in April 2012, or the Clinical Trial document published in 2009 prior to study start.

There is one minor deviation from the PhD-protocol: It was planned to define patients in the exercise group scoring 44 or less in the QOL outcome KOOS as failures and thereby fulfill the criteria for crossover to the arthroscopy group. This definition was not used in the clinical situation. The indication for arthroscopy (or reoperations) was determined by the treating orthopedic surgeon based upon the patient's history, clinical findings and radiologic exams.

